Results: Mean age of the caregivers was 34.2 ± 7.3 years, and 96% were women. Both depressive (26%) and anxiety disorders (22%) were common. Caregivers with clinically significant elevations in the anxiety or depression BSI subscales reported more asthma-related hospitalizations for the child in the past 12 months than did caregivers with lower BSI scores (all $p < 0.05$). Asthma-related hospitalizations correlated with BSI total ($r = 0.20$, $p \leq 0.01$), anxiety ($r = 0.21$, $p < 0.01$), and depression ($r = 0.16$, $p \leq 0.05$) subscale scores. Caregiver psychiatric diagnosis of an anxiety disorder (n = 36) was associated with 43% more asthma-related hospitalizations (2.0 ± 2.5 vs. 1.4 ± 1.2 , $p < 0.05$) in the child while current caregiver depression (n = 44) was associated with 50% more unscheduled clinic visits (3.0 ± 3.4 vs. 2.0 ± 2.6 , $p < 0.05$).

Significance: This study demonstrates that the Diagnostic and Statistical Manual of Mental Disorders (DSM-IV)-defined psychiatric disorders, particularly depressive disorders, are common in asthma caregivers and associated with a greater frequency of asthma-related service utilization by the child. The study also supports feasibility by demonstrating that we can enroll large numbers of caregivers in a research study.

3.3.a.ii. Pilot Study 2: Antidepressant Treatment of Caregivers of Children with Asthma Improved the Child's Asthma: This pilot study, conducted in Dallas, examined the impact of antidepressant treatment on the caregiver's depression and the child's asthma.³⁵

Methods: Eight currently depressed asthma caregivers (6 women and 2 men, mean age of 35.8 ± 6.6 years) were enrolled in this intervention study with monthly assessments for 6 months, and received algorithm-based

antidepressant treatment. The children were 5 boys and 3 girls with a mean age of 9.8 ± 3.8 years. Caregiver depressive symptoms were assessed with the Hamilton Rating Scale for Depression (HRSD)⁴⁷ and Quick Inventory of Depressive Symptomatology-Self-Report (QIDS-SR).⁴⁸ Spirometry was obtained and asthma symptoms quantified using the Pediatric Asthma Symptom Scale (PASS). Hospitalizations, emergency room visits, and unscheduled clinic visits were also assessed.

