3.3.d.iv. Asthma Severity, Control and Outcomes: Asthma outcome measures to be used in this study will adhere to the recommended asthma clinical research core outcome measures recently proposed by the NIH's Asthma Outcomes Workshop.⁶⁰ We will incorporate information on asthma exacerbations, healthcare utilization, pulmonary function, quality of life, composite control scores, and asthma symptoms into our outcome measures. Exacerbations will be assessed by caregiver report at each study visit. Exacerbation outcomes will include systemic steroid courses, asthma-specific hospitalizations, asthma-specific emergency department visits/urgent care visits, and asthma-specific intensive care unit admissions/intubations since the last appointment. Healthcare utilization relating to each child's asthma will be assessed, including asthma-specific hospitalizations, asthma-specific emergency department visits/urgent care visits, asthma-specific outpatient visits, and asthma-specific medication use. The number of asthma-specific hospitalizations, emergency department visits and unscheduled clinic appointments by the child in the prior year and during the 1 year of the intervention will be assessed by caregiver report using a calendar to facilitate recall. This information will be supplemented with data obtained directly from the child's hospital, primary physician/asthma specialist, and pharmacy records.

Spirometry data, including % predicted of FEV₁, forced vital capacity (FVC), and FEV₁/FVC ratio will be collected on the child at all study visits using a portable spirometer (EasyOne Plus, NDD Medical Technologies, Inc. Andover, MA).

As a measurement of asthma control, the Asthma Control Test (ACT) will be administered to children ages 12+ at each caregiver depression study visit and the Childhood Asthma Control Test (cACT) will be administered to children ages 5-11.^{61, 62} The ACT and cACT tools represent a continuum of asthma control assessment tools across childhood age ranges. In both tools, a score of > 19 signifies controlled disease and scores of ≤ 19 signifies uncontrolled asthma. Thus, the scores can be combined in the data analysis.

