Aim 2. Determine if improvement in depressive symptoms in caregivers of children with asthma predicts reduced unscheduled asthma-related service utilization. Separate analyses will be done for each event (ER visits, hospitalizations and unscheduled appointments). The dependent variable will be a count of the number of times the event occurred during the 52 week study period. This number will be converted to events per month to adjust for subjects who do not complete 52 weeks. The independent variables will be caregiver depressive symptoms as measured by HRSD along with site, baseline depressive symptoms, baseline asthma symptoms, and season of the year. Other baseline demographic and clinical variables (such as child's age) will be added if they improve the fit of the final model. Because the dependent variable is accumulated over the study period, caregiver HRSD will also be summarized over the study period for each subject by computing a seasonally adjusted slope of change over time during the 52 week study. All participants with two or more post-baseline HRSD measurements will be included in the analyses. Count data typically follow a Poisson distribution. Therefore, a generalized linear mixed model with Poisson link function will be used (SAS Proc GLIMMIX). Intercepts will be random effects. If an excessive number of subjects have zero events and the Poisson distribution is not appropriate (which often occurs with count data), then we will consider negative binomial models, zero-inflated Poisson models, and hurdle models. At times caregiver depression may get worse, despite treatment. Therefore, we will examine whether increases in caregiver depressive symptom severity predicts worse child asthma outcomes. The same model used above will be used here except that an indicator variable will be added to indicate if caregiver HRSD scores worsened or stayed the same during the study (zero or positive slope) versus improved (negative slope). The addition of this indicator variable will allow the relationship between change in HRSD and utilization events to differ for those who worsen or stay the same versus those who improve. This aim will be tested by the significance of this additional indicator variable. The primary analysis for this aim will use HRSD scores and ER visits (sensitive to the intervention in Pilot Study #2 and an important clinical outcome). However, similar analysis will be conducted using the QIDS-SR and STAI in place of the HRSD, and using unscheduled clinic visits and hospitalizations.

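### Aim 2 asks about reduced service use but does not commit to adjusting for the child's prior-year count of the same event, which the trial collects

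*Combined protocol and SAP*

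**What the plan says.** Section 3.4 states Aim 2 as: "Determine if improvement in depressive symptoms in caregivers of children with asthma predicts reduced unscheduled asthma-related service utilization". Four features of the model matter here.

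- **Outcome.** It is "a count of the number of times the event occurred during the 52 week study period", converted to a monthly rate. It is a level during the study, not a change from the year before.
- **Predictor.** Caregiver HRSD is summarised by "computing a seasonally adjusted slope of change over time during the 52 week study", so each family contributes one slope and one accumulated count.
- **Covariates.** The slope is entered "along with site, baseline depressive symptoms, baseline asthma symptoms, and season of the year". The next sentence adds: "Other baseline demographic and clinical variables (such as child's age) will be added if they improve the fit of the final model".
- **Random effect.** Intercepts are random.

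The missing baseline value is in hand. Section 3.3.c records hospitalizations, ER visits and unscheduled appointments over the 12 months before entry. Section 3.3.d.iv repeats that these events "by the child in the prior year and during the 1 year of the intervention will be assessed by caregiver report", with a calendar to aid recall and medical records as a supplement. Nothing in section 3.4 says how the prior-year counts will be used.

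**The concern.** The word reduced implies a comparison with the child's own earlier use, but the committed model has no baseline value of the outcome. If families with habitually high ER use also have caregivers whose HRSD falls less, then a slope and an on-study count will be associated even when improvement changes nothing. The random intercept does not help: with one count per child it absorbs overdispersion and cannot remove a stable family level. Baseline depressive symptoms and baseline asthma symptoms adjust only in part.

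The point has more weight here than in a randomized trial. Section 3.3.b describes the design as within-subject and does without a control group, yet this analysis compares families with each other. ER visits were made the primary event because they responded in Pilot Study 2, and that was a before-and-during comparison (0.30 to 0.16 per month, Table 1).

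What is at stake is a spurious finding for Aim 2 or, if the correlation runs the other way, a masked one. Where there is no such correlation, what is lost is precision.

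**Working it through.** **1. The plan's own power figure.** For 10 predictors and N = 175 the Power paragraph gives f² = 0.10 at 80% power. Using the noncentral F with λ = f²N, u = 10, v = 175 − 10 − 1 = 164 and α = 0.05 (assumed; not stated), the minimum f² is 0.098, and power at 0.10 is 0.810. The figure reproduces as a joint test of all ten predictors. An eleventh predictor moves the minimum to 0.102 and power at 0.10 to 0.791. For a single coefficient the minimum f² is 0.045 either way. Adding the count therefore costs almost nothing.

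**2. Inputs for the bias.** From the documents: N = 175, and pilot ER rates of 0.16 and 0.30 per month, so 12 × 0.16 = 1.92 and 12 × 0.30 = 3.6 per year. Assumed, because the documents do not give them:

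- s, the SD of log usual use between families;
- ρ, the correlation of usual use with HRSD slope;
- r, the correlation of usual use with baseline asthma symptoms;
- how stable usual use is from year to year.

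The pilot gives only a rough hint of between-family variance: SD 12 × 0.21 = 2.52, variance 6.35, excess over Poisson 6.35 − 3.6 = 2.75, and 2.75/3.6² = 0.21. That rests on eight families and treats the pilot baseline as a 12-month window, which Pilot Study 2 does not state. A range of 0.21 to 1.0 was used in one set of simulations. In the other, s ran from 0.5 to 1.0.

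**3. Check by hand, no true effect, count left out.** Take s = 0.8, r = 0.3, ρ = 0.2, mean 1.92.

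- Spurious log rate ratio per SD of slope: sρ(1 − r²)/(1 − ρ²r²) = 0.8 × 0.2 × 0.91/0.9964 = 0.146, a rate ratio of 1.157 (simulated: 1.152).
- Share of usual use explained: R² = (ρ² + r² − 2ρ²r²)/(1 − ρ²r²) = 0.1228/0.9964 = 0.123.
- Dispersion: φ = 1 + 1.92 × [exp(0.64 × 0.877) − 1] = 2.45.
- SE: √[2.45/(175 × 1.92 × 0.9964)] = 0.0855, so z = 0.146/0.0855 = 1.71.
- Chance of p < 0.05: Φ(1.71 − 1.96) = 0.40 (simulated: 40%).

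**4. Simulated false-positive rates.** Dispersion-scaled Poisson, stable family rates, r = 0.3, s = 0.5 to 1.0, mean 1.92 or 3.6, 2,000 runs per setting, adjustment by log(count + 0.5). The last two columns widen the range to other settings, including variance 0.21 to 1.0, log(count + 1), and usual use correlated only 0.7 across years.

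| ρ | Count out, stable rates | Count in, stable rates | Count out, all settings | Count in, all settings |
|---|---|---|---|---|
| 0 | 5-8% | 5-7% | near nominal | near nominal |
| 0.1 | 12-19% | 7-10% | 8-19% | 5-10% |
| 0.2 | 27-48% | 13-20% | 17-48% | 8-20% |
| 0.3 | 54-82% | 23-37% | 25-82% | 11-37% |

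The lower ends come from less stable family rates and shift by a few points with how that instability is modelled. Raising r to 0.5 at s = 0.8 and ρ = 0.3 still left 64-71% without the count.

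**5. Precision with no confounding.** With a true rate ratio of about 1.22 per SD of slope and stable rates, two simulations gave these powers without and with the count: 84% to 87% and 88% to 90% (variance 0.21); 72% to 85% and 80% to 90% (0.5); 58% to 80% and 61% to 85% (1.0).

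**6. The fit clause.** The plan does not define improved fit. Reading it as p < 0.05 for log(count + 1), and assuming the count is offered, it was kept in 97-100% of runs with stable rates. At a year-to-year correlation of 0.7 it was kept in 68-82% (variance 0.21) and 98-100% (0.5 to 1.0). False positives were within 2 points of mandatory adjustment throughout.

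**The case against.** The strongest reply is the fit clause. A prior-year count is a baseline clinical variable and a strong predictor, and step 6 shows that a reasonable rule would nearly always keep it. A reader might infer from the table that the plan itself runs a false-positive rate of 40% or more. The documents do not support that: those rates describe a model that leaves the count out, and the plan permits it in. What survives is that the clause does not name the count (child's age is its only example), states no criterion, and could adjust the three event models differently.

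A reader might also infer that Aim 2 compares usual levels of use and not a reduction. That is too absolute. Baseline depressive and asthma symptoms adjust in part, and the test stays near its nominal level when slope and usual use are unrelated. Overlap may be greater still if baseline asthma symptoms means the CASI, which has an exacerbations domain (section 3.3.d.iv), but Aim 2 names no instrument.

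Finally, Pilot Study 1 might be read as proof of the confounding. It reports that "current caregiver depression (n = 44) was associated with 50% more unscheduled clinic visits". That concerns depression level and not change, clinic visits and not ER visits, and depressed against non-depressed caregivers, whereas everyone enrolled here has current MDD. The reported correlation of the depression subscale with hospitalizations, 0.16, is also with level. These findings make a link plausible; they do not give its size.

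**Conclusion.** The point holds as a gap in pre-specification. Aim 2 claims a reduction, models an on-study level, and leaves the baseline value of its own outcome to an undefined, data-driven rule. If the count stays out, usual use and reduction cannot be told apart. The resulting false-positive rate runs from near nominal at correlation 0 to as high as 82% at 0.3, and adjustment brings it down to at most 37%. The correlation, the between-family spread and the year-to-year stability are all assumptions, so these figures show sensitivity and are not an estimate for this trial. The gain in precision does not depend on confounding, but it does depend on the between-family spread: small at variance 0.21, and more than 20 percentage points at 1.0. Since adjustment is nearly free and the data are already collected, the change is worth making.

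**What to change.** In section 3.4, Aim 2, name the prior-12-month count of the same event, for example as log(count + 1), as a fixed covariate in every model: ER visits (primary), hospitalizations and unscheduled appointments. Include the model with the worsening indicator. Keep the count regardless of fit, and leave the fit clause for the remaining optional variables.

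The cost is one sentence in the analysis plan and one degree of freedom per model (detectable joint f² 0.098 to 0.102). The limitation should be stated alongside: prior-year counts rest partly on caregiver recall, and a single noisy count reduces this confounding without removing it, so a positive Aim 2 result would still need cautious wording.

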3.3.a.viii. Summary of Findings from Preliminary Studies and the Literature: 1) Our pilot studies show that we can successfully enroll and retain caregivers and children with asthma in research studies. 2) Our pilot data suggest that psychiatric disorders, especially depression, are very common in caregivers of children with asthma. 3) Caregiver depression is associated with more severe childhood asthma and greater service utilization. 4) The literature and [name] and [name]'s preliminary studies suggest that caregiver depression contributes to worse asthma in the child, possibly mediated through stress/depression pathways. 5) The literature suggests that poor adherence is also a likely mediator between caregiver depression and child asthma. 6) Based on our pilot data, treatment of depression in the caregiver was associated with improvement in caregiver depression and a reduction in asthma symptom severity and service utilization by the child.

Given these findings, a study of caregivers and their children with asthma is proposed. **We will test these hypotheses: 1) Improvement in caregiver depression leads to subsequent improvement in the child's asthma control, quality of life, and service utilization. 2) Improved adherence and/or decreased child anxiety/depression mediates the effect of improved caregiver depression on child asthma outcomes.**

To test these hypotheses depressed caregivers will be offered algorithm-based antidepressant treatment by the research psychiatrists, and the impact of changes in caregiver depression on asthma in the child will be examined for 52 weeks (1 year). Mediating pathways linking caregiver depression and the child's asthma will be examined.

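### Aim 2 relates a 52-week HRSD slope to ER visits in the same 52 weeks, so it cannot show that caregiver improvement came first and can be significant under reverse causation alone

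*Combined protocol and SAP*

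**What the plan says.** Section 3.4, Aim 2, defines the outcome: "The dependent variable will be a count of the number of times the event occurred during the 52 week study period". The count is then rescaled to a monthly rate to allow for early leavers. The predictor comes from "computing a seasonally adjusted slope of change over time during the 52 week study", and the reason given is "Because the dependent variable is accumulated over the study period, caregiver HRSD will also be summarized over the study period for each subject". HRSD enters "along with site, baseline depressive symptoms, baseline asthma symptoms, and season of the year", and other baseline variables may be added if they improve fit. No lag, landmark or ER history is listed. On the main outcome: "The primary analysis for this aim will use HRSD scores and ER visits".

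A second step adds an indicator for caregivers whose slope is zero or positive: "This aim will be tested by the significance of this additional indicator variable".

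Hypothesis 1 in section 3.3.a.viii reads "Improvement in caregiver depression leads to subsequent improvement in the" child in three areas, of which service utilization is one. Aim 2's own heading is milder and says only that improvement predicts reduced utilization. Section 3.3.d.iv has caregivers report exacerbation outcomes, including emergency and urgent care visits, at each visit for the period "since the last appointment".

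**The concern.** Exposure and outcome are both accumulated over one window, so an ER visit in month 2 is predicted in part by HRSD scores up to month 12. If a child's ER visits lower the caregiver's mood, families with more visits will tend to show less HRSD improvement, which is the pattern Aim 2 would read as support.

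The protocol takes this reverse path seriously. Section 3.1.a regards it as likely that severe asthma in the child adds to caregiver depression. The study has no control arm, and section 3.3.b relies on cross-lagged models to show that caregiver improvement came before asthma improvement. Time order is therefore the design's main defence against the reverse reading, and Aim 2 discards it for utilization. At stake is whether a positive ER result can be reported as support for the utilization part of hypothesis 1.

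**Working it through.** **1. The plan's own figures.** The Power paragraph gives detectable effects at N = 175 and 80% power of f² = 0.10 (10 predictors) and 0.31 (78 paths). Take a joint F test of u predictors with v = 175 − u − 1 and noncentrality 175 × f², at an assumed two-sided alpha of 0.05 (none is stated for Aim 2).
- u = 10, v = 164: f² = 0.098; power at 0.10 is 81.0%.
- u = 78 = 13 × 12 / 2, v = 96: f² = 0.309; power at 0.31 is 80.2%.

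Both reproduce. Neither bears on time order.

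**2. Does the test use timing?** Write Y_ik for ER visits of child i in 4-week interval k, s_i for the 52-week HRSD slope, H_i0 for baseline HRSD and A_i for baseline asthma. The model is log E(Σ_k Y_ik) = a + b·s_i + c·H_i0 + d·A_i + …. Visits enter only through their sum, so with HRSD held fixed their dates are irrelevant. In one simulated data set the slope coefficient was 0.334 (p = 0.044) with visits as simulated, with all moved to the first interval, and with all moved to the last.

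**3. Reverse causation only.** HRSD has no effect on ER visits in these simulations.
- Visits: Poisson, 0.2 per 4 weeks, with between-child log-SD 0.6. The pilot (Table 1) had 0.30 per month at baseline and 0.16 at exit.
- Carry-over: C_ik = ρ·C_i,k−1 + δ·Y_ik, also run over six pre-baseline periods.
- HRSD: H_ik = b_i + t_i·k + C_ik + error, with b_i of mean 20.9 and SD 4, t_i of mean −0.5 per visit and SD 0.35, and error SD 3.5.
- Analysis: quasi-Poisson of total visits on slope, baseline HRSD and a noisy baseline asthma score. Site and season were not simulated.

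δ, ρ, the between-child spread and the child-specific ER trend are assumptions. With δ = 2, ρ = 0.6 and a trend, mean HRSD went from 21.9 (SD 5.5) to 15.6 (SD 7.2). The six-month pilot went from 20.9 (5.8) to 15.5 (7.9).

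Percentage of trials significant in the hypothesised direction (nominal 2.5%), N = 175, 400 trials per cell:

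| Child ER trend SD | ρ | δ=0 | δ=1 | δ=2 | δ=3 | δ=4 |
|---|---|---|---|---|---|---|
| 0 | 0.6 | 2.5 | 6.5 | 19.8 | 32.0 | 47.2 |
| 0 | 0.9 | 3.0 | 68.0 | 99.3 | 100 | 100 |
| 0.7 | 0.6 | 2.0 | 28.2 | 64.0 | 86.3 | 93.8 |
| 0.7 | 0.9 | 4.5 | 92.2 | 100 | 100 | 100 |

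At the planned enrolment of 196 (trend, ρ = 0.6), δ = 1 and 2 gave 26% and 70%. Other set-ups with ρ = 0.7 and N = 175 gave 24–63% at 2 points and 66–94% at 4 points, against 3–6% with no reverse effect.

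**4. Worsening indicator.** Over the cells with δ = 1 to 4, it rejected in 4% to 34% (two-sided, nominal 5%).

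**5. Time-ordered alternatives, still with no HRSD effect.**
- Landmark (HRSD slope over weeks 0–24, ER count over weeks 24–52), adjusted for earlier ER visits: about 2–10%. Without that adjustment: about 5–68%, so separating the windows is not enough.
- Interval model (ER count on HRSD at the opening visit, with prior ER rate), ρ = 0.7: three sets of runs gave 0–19%, 6–15% and 14–34%.
- Interval model with HRSD split into a 52-week family mean and visit deviations: the mean term was falsely significant in 49–100%, and the deviation term in the wrong direction in 60–99%.

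**6. Power.** With a true forward effect of 0.06 log-rate per HRSD point, power was 55% for the planned slope test and 48% for the adjusted landmark (300 trials).

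**The case against.** **Direction is tested elsewhere.** Aim 1 fits cross-lagged models with explicit reverse paths for CASI, ACT and steroid bursts. CASI has an exacerbation domain, and the outcome list is given as examples. This is true, and it means the study as a whole is not blind to direction. But no cross-lagged model is written for ER visits, hospitalizations or unscheduled appointments. Aim 4 names utilization and refers its first-to-third link back to Aim 1, which does not list those events. The Power paragraph puts Secondary Aim 2 both in the 10-predictor group and in the group with 13 measurement occasions. A reader might infer a lagged utilization model from that, but a numbering conflict does not specify one.

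**Aim 2 claims only prediction.** This also stands as to its heading. The claim of order comes from hypothesis 1, and Aim 2 is the only specified test of its utilization part.

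**The reverse effect is unproven.** Section 3.1.a also cites a path analysis in which baseline asthma symptoms did not predict later maternal depression. The documents give no figure for HRSD points per ER visit. The pilot's whole treatment change was 20.9 − 15.5 = 5.4 points, so δ = 4 gives one visit 4 / 5.4 = 74% of that. The high cells should not be taken as forecasts.

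**A stronger reading is tempting:** that the Aim 2 test will be significant whenever reverse causation exists. The documents do not support it. With small, short-lived effects the rate was about 7%, and the indicator test was seldom significant.

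**Conclusion.** The concern holds in a limited form. That the Aim 2 result is unaffected by when ER visits occurred follows from the model and needs no assumption; the planned analysis therefore cannot establish the order in hypothesis 1. That it can be significant under reverse causation alone is also shown, and adjustment for baseline HRSD and a baseline asthma marker did not remove the problem.

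The frequency is not a property of the plan. The range of about 7% to 100% rests on assumed values for the effect of a visit, its persistence and the drift in each child's ER rate. With no reverse effect the test stayed close to nominal (2–5%). This is a change that should be made before analysis; it does not invalidate Aims 1 or 3.

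**What to change.** Make the primary Aim 2 analysis time-ordered, and name one of these forms in the SAP before the data are examined:

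- **Interval:** the ER count in each between-visit interval, modelled on HRSD at the visit that opens it, allowing for repeated counts per child.
- **Landmark:** the HRSD slope over weeks 0–24 against the ER count over weeks 24–52.

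In either case adjust for ER visits before the window, baseline HRSD, baseline asthma, site and season, with log exposure time as offset. The adjustment for earlier ER visits is essential. Do not split HRSD into a 52-week family mean and deviation, because that mean contains scores taken after the visits being modelled; any person-level HRSD summary should use only visits up to the start of the interval.

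Keep the 52-week slope model as descriptive. Word the conclusion as *precedes*, not *causes*, since some reverse-causation bias can remain. Section 3.3.d.iv lists hospitalizations in the same per-visit report; for unscheduled clinic appointments it mentions only a recall calendar and records, so the SAP should say how their dates are kept.

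Cost: SAP text, a longer analysis file, sparser counts per window and a modest loss of power. No new data on ER visits are needed. The power figures come from one scenario for the landmark form; no power was computed for the interval form.
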